1.2 Trial Rationale

Traditionally palliative care services are largely provided in the UK by local and national independent, charitable organisations. Thus it is important for both the NHS and other providers to undertake research into new models of care in advanced cancer in which anticancer treatment and patient/family directed, supportive and palliative care services are simultaneously provided^[4]. The National Cancer Action Team has recently recommended that all patients with cancer should receive Holistic Needs Assessment (HNA) at key points of their trajectory from diagnosis, after primary treatment, through continuing disease into end of life care or into survivorship^[5].

As patients with advanced NSCLC often have a high symptom burden at diagnosis this patient group is in particular need of HNA at the point of diagnosis as well as through their ongoing care. Holistic needs include not only physical symptoms but also psychological, social, spiritual, financial issues; problems with independent living; concerns about treatments and side-effects; and information needs. Many services are not yet using any formal means of assessing holistic needs though there a range of HNA tools available with the Distress Thermometer/Concerns Checklist or the Sheffield Profile for Assessment and Referral for Care (SPARC) most commonly used in the UK^[6].

The SPECIAL trial has been designed to address the question of whether early referral to palliative care services in the UK achieves the same range of benefits, including quality of life and survival, as those observed in the Temel *et al.* (2010)^[3] US study, given that the provision of palliative care is so different in the two countries. It further asks the question whether a formal holistic needs assessment enhances the referral to palliative care.

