2.2.2 Randomised Controlled Trial Outcome Measures

The primary objective is to compare the two treatment arms in terms of the two co-primary outcome measures:

- (i) Global Health Status Score (GHSS) at three months post randomisation, and
- (ii) Quality-Adjusted Survival time (QAS) over six months

Secondary outcome measures:

- Overall survival
- Anxiety/depression
- Pain
- Quality of Life
- Cost-effectiveness
- Resource use
 - Days spent in hospital/hospice
 - Admission to an Intensive Therapy Unit (ITU)
 - Use of medical interventions in last month of life (see Appendix 1 for definitions)
 - Use of cardio-pulmonary resuscitation (CPR)
 - Compare the arms of SPARC sub-randomisation in the early palliative care group to see if HNA as an intervention is associated with better outcomes

The following will be measured from trial entry at each clinic visit the patient attends until the end of the trial or death:

- Health related quality of life using EQ-5D-5L and European Organisation for Research and Treatment of Cancer (EORTC) QLQ C30/LC13/BM22
- Hospital Anxiety and Depression Scale (HADS)
- HNA using SPARC (see Appendix 2)
- Modified Glasgow Prognostic Score (mGPS) (see Appendix 3)
- Nurse-rated and patient-rated ECOG
- Montreal Cognitive Assessment scale (MoCA) (see Appendix 4)

Additionally carers will receive:

- Short form-12® (SF-12®) health related quality of life questionnaire
- Family caregiver satisfaction of palliative care services questionnaire (FAMCARE-2)
- The CODE™ instrument

The modified Glasgow Prognostic Score will be used primarily as a prognostic and stratification measure at baseline. It will be repeated again at the key primary end-points of three months and six months to test for its utility as a prognostic score later in the disease ^{[7],[8]}.

In order to control for effects of co-morbidity on patients' physical condition and holistic needs, the Scottish Lung Cancer Co-Morbidity Index (see Appendix 5) will also be used at baseline^[9]. Neither this co-morbidity index nor the mGPS are outcome measures but do represent important potential antecedent variables which could influence symptoms and other holistic needs as well as survival, so will be used in the statistical analysis to help explain variations in the patients' outcomes.

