19.2.2.1 Primary Outcome Measures

Global health status score: The two treatment groups will be compared in terms of this outcome measure at three months using a t-test. It is recognised that there will be some variation in the timing of the QoL assessments and a window of two weeks either side of the planned three month assessment will be acceptable. This part of the analysis will only be carried out in those patients who are alive and well enough to complete a questionnaire at three months (i.e. a complete case analysis) and therefore it is a conditional analysis but it will be intention-to-treat in the sense of including patients under their randomised allocation.

QAS time: Treatment groups will be compared using a t-test. The advantage of this analysis is that it is intention-to-treat, dealing with missing data due to death and dropout and therefore including all randomised patients in the analysis.

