19.2.2.2 Secondary Outcome Measures

The following measures will be reported by treatment arm:

Overall survival: A Kaplan Meier plot of overall survival will be reported along with hazard ratio and median survival (both with 95% CI).

Anxiety/depression: The average change in HADS score from baseline to six months will be compared using a t-test (or non-parametric alternative). The mean area under curve will also be compared using a t-test.

Pain: The average change in pain domain score from baseline to six months will be compared using a t-test (or non-parametric alternative). The mean area under curve will also be compared using a t-test.

Cost Effectiveness:

- Days spent in hospital/hospice Mean (95% CI) stay and overall stay duration and frequency
 of hospital/hospice say durations will be compared using a t-test (or non-parametric alternative).
 The number of patients admitted but not discharged will be reported. The proportion of patients
 spending time in hospital/hospice will be reported.
- Use, or not, of medical interventions in last month of life A line-listing of medical interventions including, where applicable, intervention type, dose, duration and other pertinent metrics. The period over which these interventions are to be observed will also be reported (some may not have been followed for a month).

ITU admission: The number of ITU visits, and the number of patients making those visits along with the mean (95% CI) length of each visit, and the mean (95% CI) of patients overall ITU duration.

Use of CPR: The proportion of patients requiring CPR and the average number of resuscitations required per patient will be reported.

For each of the questionnaire based outcome measures the mean (sd) score will be reported by visit.

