19.2.5.1 Global Health Status Score

Assuming a median survival time in these patients of six months and an exponential distribution, it is expected that 70% of randomised patients will be alive at three months. Experience in the BTOG2 trial shows that we would expect high compliance in these remaining patients, so we assume a further 5% dropout for reasons other than death, giving a total loss of 35% of randomised patients. From literature, GHSS in patients with metastatic NSCLC is 58.8 with standard deviation of 23 points and data from the stage IV patients in the BTOG2 trial shows similar values with a mean GHSS at baseline of 61.5 and standard deviation (SD) of 23. A difference of seven points between treatment groups at three months, which is a standardised effect size of 0.3, is considered to be realistic and clinically relevant. Assuming a 5% two-sided significance level and 80% power the analysis requires a total of 342 patients to detect this level of difference and thus 525 randomised patients. For 90% power the analysis requires a total of 456 patients and thus 700 randomised patients.

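### The co-primary GHSS test compares only patients alive and able to complete the form at three months, discards living non-completers who may have earlier scores, and has no companion analysis of GHSS that counts deaths

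*Protocol*

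**What the plan says.** Section 2.2.2 names "Global Health Status Score (GHSS) at three months post randomisation, and" quality-adjusted survival (QAS) over six months as the two co-primary outcomes. Section 19.2.2.1 compares GHSS by t-test, within two weeks either side of the three-month visit. The analysis is to "only be carried out in those patients who are alive and well enough to complete a questionnaire at three months", and the protocol describes it as complete case. It adds that "therefore it is a conditional analysis but it will be intention-to-treat in the sense of including patients under their randomised allocation". The QAS paragraph that follows includes every randomised patient. Section 19.2.1.1 sets QAS values to zero from death and imputes missing ones.

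The sample size in section 19.2.5.1 rests on the same restriction: "it is expected that 70% of randomised patients will be alive at three months", "so we assume a further 5% dropout for reasons other than death, giving a total loss of 35% of randomised patients". Section 19.1.1 sets a looser feasibility target, completion of the three-month GHSS by 80% of survivors.

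Section 1.2 asks whether early referral "achieves the same range of benefits, including quality of life and survival" seen in the earlier US trial, and section 3.2 says the randomised stage is not blinded. The QLQ-C30 is in every follow-up booklet (Appendix 8). ECOG status is recorded at each three- or four-weekly visit (section 7.2.2.2), and mGPS is measured at baseline (section 7.2.2.1).

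**The concern.** Being alive and well enough at three months is determined after randomisation and depends on health. Randomisation makes the full arms comparable. It does not make the completers comparable unless survival and completion are similar in both arms, and a difference in survival is one of the things the trial sets out to detect.

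If early referral keeps frailer patients alive, that arm contributes low scores from patients whose counterparts under standard care have died, and a real GHSS benefit is understated. If frail patients in the early-referral arm return fewer forms, the shift goes the other way and favours that arm.

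Living patients without a three-month form raise a separate issue. Many will have an earlier GHSS and ECOG status, and all should have a baseline mGPS, but the complete-case rule uses none of this. The protocol specifies imputation for QAS and rules it out for GHSS.

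**Working it through.** **1. The plan's own figure.** A two-sample t-test with difference 7, SD 23, two-sided 5% and 1:1 allocation needs 342 patients for 80% power and 456 for 90%, as stated. Allowing for 35% loss, 342/0.65 = 527 and 456/0.65 = 702, within two patients of the stated 525 and 700. Exponential survival with a six-month median gives exp(-3 ln 2/6) = 0.707 alive at three months, against the stated 70%. The arithmetic is sound.

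**2. Who is left out.** 0.35 × 525 = 184 patients: about 158 through death (0.30 × 525) and about 26 for other reasons (0.05 × 525). The plan therefore assumes 0.65/0.70 = 93% completion among survivors.

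**3. Completion at the feasibility target.** With 80% of survivors completing, 0.70 × 0.80 = 0.56. Total loss is 44%, 294 of 525 are analysed, and power for seven points is about 74% before any shift.

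**4. Shift from a survival effect (illustration).** From the plan: S_A = 0.707, SD 23, 525 randomised, 5% non-death loss. Assumed: GHSS and the liability to survive are jointly normal with correlation ρ; the survival hazard ratio is HR; the 5% loss is unrelated to score.

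- S_B = S_A^HR
- c = Φ⁻¹(1 − S) and λ = φ(c)/S
- Survivors' mean is raised by ρ × 23 × λ
- Survivors' SD = 23 × √(1 − ρ²λ(λ − c))
- Completers per arm = 262.5 × (S − 0.05)

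Standard care: c = −0.545, λ = 0.486, mean raised by 3.36 (ρ = 0.3) or 5.59 (ρ = 0.5). Early referral at HR 0.8: S_B = 0.758, λ = 0.412, raised by 2.84 or 4.74. At HR 0.7: S_B = 0.785, λ = 0.373, raised by 2.57 or 4.29. The shift is early referral minus standard care, taken before rounding. Power is for a difference of 7 plus the shift.

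| HR | ρ | Shift (points) | Completers | Power, survivors' SD | Power, SD held at 23 |
|---|---|---|---|---|---|
| 0.8 | 0.3 | −0.51 | 358 | 78% | 76% |
| 0.8 | 0.5 | −0.85 | 358 | 77% | 71% |
| 0.7 | 0.3 | −0.78 | 365 | 75% | 73% |
| 0.7 | 0.5 | −1.31 | 365 | 71% | 65% |

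The survivors' SD in this model is 22.5 (ρ = 0.3) or 21.5 to 21.7 (ρ = 0.5). With that SD and no survival effect, power would be 82% or 85%, so the like-for-like loss is about 5 to 15 percentage points. At HR 0.9 the shift is only −0.25 to −0.42.

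**5. The opposite direction.** Apply the same formula to completion instead of survival, with 65% completing under standard care. If 60% complete under early referral, the shift is +0.51 (ρ = 0.3) to +0.85 (ρ = 0.5). If completion is equal and the selection mechanism is the same, the shift is zero.

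**The case against.** The protocol does not hide the restriction. It calls the analysis conditional, limits the intention-to-treat description to the randomised allocation, and pairs GHSS with a co-primary that includes every death. Overall survival is also reported by arm. This stands, and it is why the qualified intention-to-treat phrase needs no deletion. It does not make the GHSS completers comparable, and GHSS is powered and tested in its own right.

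The seven points can be read as the difference among those analysed. On that reading the stated power is correct on its own assumptions, and the shift above measures only the distance from the effect of early referral in a common set of patients. This also stands: the power figures are an illustration and show no error in the sample size.

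The correlations and hazard ratios are assumed. The protocol gives neither, and at HR 0.9 the shift is small.

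A reader might infer more than the text supports:

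- **All 35% are lost for health reasons.** The figure is a planning assumption, and the 5% is described only as loss not due to death.
- **Larger power losses.** Holding the sample at 342 and the SD at 23 gives lower power, but the same model keeps more patients alive and narrows the survivors' SD.
- **The same rule for HADS and pain.** Section 19.2.2.2 says "The average change in HADS score from baseline to six months will be compared using a t-test" and treats pain likewise, but states no survivor-only rule. It adds an area-under-curve comparison for both, and handling of missing values may be left to the SAP.

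The SAP was not available and may contain sensitivity analyses. The primary analysis set, however, is fixed in the protocol.

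**Conclusion.** The point holds as a weakness in how a co-primary analysis is fixed. The GHSS test selects on survival and fitness after randomisation, discards living non-completers for whom relevant data are collected, and section 19.2.2.1 sets no analysis that takes GHSS and death together. With "giving a total loss of 35% of randomised patients" planned, and 44% at the feasibility completion target, the selection is not marginal.

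Under the assumed correlation of 0.3 to 0.5 and hazard ratio of 0.7 to 0.8, the difference shifts by −0.5 to −1.3 points (7% to 19% of the seven-point effect), and power is roughly 71% to 78% against the planned 80%. The documents do not establish that the result will be biased, or in which direction. That depends on survival and completion by arm, and if these are similar the effect is negligible.

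**What to change.** In section 19.2.2.1:

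- **(a) Living non-completers.** State the GHSS target as the difference at three months among patients alive then. Replace the complete-case rule for living patients without a three-month form by a likelihood-based repeated-measures model, or by multiple imputation, using earlier GHSS, ECOG and baseline mGPS. Impute nothing beyond death. Add a delta-adjusted sensitivity analysis in which non-completers score worse than predicted.
- **(b) Deaths.** Because (a) still compares survivors, pre-specify a supportive analysis of all randomised patients in which death before three months ranks below any living score. Report it with three-month survival and completion by arm. It supports interpretation and need not be a condition for claiming a GHSS benefit.

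The cost is protocol and SAP wording and some programming. The data are already collected and no more patients are needed. The drawbacks are a slightly more complex primary model and two GHSS results to explain if they differ.

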19.2.2.2 Secondary Outcome Measures

The following measures will be reported by treatment arm:

Overall survival: A Kaplan Meier plot of overall survival will be reported along with hazard ratio and median survival (both with 95% CI).

Anxiety/depression: The average change in HADS score from baseline to six months will be compared using a t-test (or non-parametric alternative). The mean area under curve will also be compared using a t-test.

Pain: The average change in pain domain score from baseline to six months will be compared using a t-test (or non-parametric alternative). The mean area under curve will also be compared using a t-test.

Cost Effectiveness:

- Days spent in hospital/hospice Mean (95% CI) stay and overall stay duration and frequency
 of hospital/hospice say durations will be compared using a t-test (or non-parametric alternative).
 The number of patients admitted but not discharged will be reported. The proportion of patients
 spending time in hospital/hospice will be reported.
- Use, or not, of medical interventions in last month of life A line-listing of medical interventions including, where applicable, intervention type, dose, duration and other pertinent metrics. The period over which these interventions are to be observed will also be reported (some may not have been followed for a month).

ITU admission: The number of ITU visits, and the number of patients making those visits along with the mean (95% CI) length of each visit, and the mean (95% CI) of patients overall ITU duration.

Use of CPR: The proportion of patients requiring CPR and the average number of resuscitations required per patient will be reported.

For each of the questionnaire based outcome measures the mean (sd) score will be reported by visit.

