6.2 Randomised Controlled Trial - Randomisation

To randomise a patient into the RCT complete a Randomisation Form and call the CRCTU using the number below.

2 [name]

9.00 am till 5.00 pm Monday to Friday

The CRCTU Randomisation Office will be closed on Bank Holidays and University of Birmingham closed days.

Sites will be informed of forthcoming closures in advance.

The following information should be provided:

- Name of site and investigator
- Patient's initials
- · Date of birth
- · Confirmation of eligibility
- Date of patient consent
- Whether the patient has consented to the optional aspects of the study. If the patient has consented to the Qualitative Interviews their full name and telephone number will be collected)
- Details of carer consent including their initial's, whether they have consented to the qualitative interviews. If the patient has consented to the Qualitative Interviews their full name and telephone number will be collected)

Patients will be randomised using a computerised minimisation technique. Stratification variables include:

- Site
- Age (<50 years, ≥50 year)
- The presence or absence of brain metastases
- mGPS (scores 0, 1 or 2)

Patients will be randomised one-to-one to the following arms:

- Arm A: Standard Care
- · Arm B: Early referral to SPC

Patients allocated to Arm B will undergo a second randomisation (1:1) to:

- Arm B1: Sites Standard SPC
- Arm B2: Sites Standard SPC + SPARC

Patients will be issued with a unique Trial Number which should be used on all correspondence with the Trial Office.

The completed Randomisation Form, Eligibility Checklist and a copy of the Informed Consent Form should be sent to the Trial Office.

With the patient's prior consent their GP should also be informed that they are taking part in the trial. A RCT GP Letter is provided electronically for this purpose.

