19.2.1.2 Secondary outcome measures

A secondary objective will be to compare the arms of SPARC sub-randomisation in the early palliative care group to see if HNA as an intervention is associated with better outcomes.

Other secondary outcome measures are defined as:

Overall survival: defined as the time from randomisation to death (due to any cause) or to date last seen for those not known to have died.

Anxiety/depression: will be measured using the HADS questionnaire and scored as per the HADS algorithm.

Pain: based on the EORTC QLQ-C30 and -LC13 questionnaire pain domains.

Health Economics; Cost Effectiveness and Resource Use

- Days spent in hospital/hospice: obtained from patient records. Duration defined as time from admission to discharge.
- Use, or not, of medical interventions in last month of life: details of further interventions administered during the last month of life will be obtained from patient records. The patient subgroup will be defined as those for which death was observed.
- **ITU admission:** the number of patients admitted, the frequency and duration of visits will be obtained from patient records. Duration is defined as the time from admission to discharge from intensive treatment unit.
- Use of CPR: obtained from patient records.

QoL: Health related quality of life will be assessed using EQ-5D-5L and EORTC QLQ C30/LC13/BM22 instruments. The instruments will be scored as per the associated algorithm.

Memory and cognitive ability: will be assessed for consenting participants using administration of the MoCA. The instruments will be scored as per the associated algorithm.

mGPS: will be assessed at baseline, 3 and 6 months. The instruments will be scored as per the associated algorithm.

Secondary outcomes pertaining to family care-givers include:

Health Survey: assessed using the SF-12®. The instruments will be scored as per the associated algorithm.

Satisfaction with participant's end of life care: assessed using the CODE™ instrument and scored as per the associated algorithms.

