19.2.2 Analysis of Outcome Measures

Full details will be specified in a Statistical Analysis Plan but an outline of the planned analyses is provided below.

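### Read naturally, Section 19.2.2.2 tests and puts intervals on length per stay or visit, though patients are randomised and can have several stays

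*Protocol*

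**What the plan says.** Section 6.2 makes the patient the unit of allocation: "Patients will be randomised one-to-one to the following arms".

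For days in hospital/hospice, Section 19.2.1.2 states "Duration defined as time from admission to discharge", which describes a single admission. The analysis in Section 19.2.2.2 then names "Mean (95% CI) stay and overall stay duration and frequency" and continues "of hospital/hospice say durations will be compared using a t-test (or non-parametric alternative"). The mean stay is thus listed apart from the overall duration and the frequency.

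The ITU sentence in the same section has the same structure and is explicit about the unit. It first reports "The number of ITU visits, and the number of patients making those visits". Visits are counted separately from patients, so repeat visits are foreseen. Its second half then asks for two quantities, one per visit and one per patient: "mean (95% CI) length of each visit, and the mean (95% CI) of patients overall ITU duration". No between-arm test is named for ITU.

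Section 19.2.2 introduces all this as an outline: "Full details will be specified in a Statistical Analysis Plan but an outline of the planned analyses is provided below". No method for several stays by one patient is mentioned.

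**The concern.** Stays by the same patient share that patient's disease, symptoms, home circumstances and local service, so their lengths are likely to be correlated. An ordinary t-test or CI on individual stays counts each stay as new information. The standard error is then too small. A rank test on individual stays assumes the same independence and does not cure this.

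There is a second, lesser problem. A mean over stays counts frequently admitted patients many times and never-admitted patients not at all, so it does not compare the groups as randomised. The protocol itself expects some patients never to be admitted, because it plans to report the proportion who spend time in hospital or hospice.

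Days in hospital/hospice is a named secondary outcome and bears on the Section 2.1.3 question of whether early referral moves resource use out of hospitals. A chance difference in length of stay could be reported as an effect of early referral, or an ITU interval could look more precise than it is.

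**Working it through.** **What the protocol supplies.** It states no standard deviation, number of stays, within-patient correlation or power for the stay analyses, so there is no figure of its own to reproduce here. The co-primary sample sizes do reproduce with one value per patient. A t-test calculation gives 342 and 456 analysed for a 7-point difference with SD 23, and 506 and 676 for a difference of 0.5 with SD 2 (80% and 90% power). Those analyses do not have this problem.

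**Inputs.** Allocation is 1:1 (Section 6.2) and the minimum sample is 525 (Section 19.2.5). The 5% two-sided level is taken from the sample size section, since none is stated for secondary tests. The number of stays per admitted patient, *m*, and the intraclass correlation of stay length, ICC, are assumptions.

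**Formulas**, for equal numbers of stays per patient:

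- Design effect: DE = 1 + (m − 1) × ICC
- Naive CI width as a fraction of the correct width: 1/√DE
- Actual rejection rate of a nominal 5% test: 2 × [1 − Φ(1.96/√DE)]

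**Results:**

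| m | ICC | DE | CI width ratio | Actual rejection rate | Simulated rate |
|---|---|---|---|---|---|
| 1 | any | 1 | 1.00 | 5.0% | not run |
| any | 0 | 1 | 1.00 | 5.0% | 4.7% to 5.1% |
| 1.5 | 0.1 | 1 + 0.5 × 0.1 = 1.05 | 0.98 | 5.6% | 6.1% |
| 2 | 0.3 | 1 + 1 × 0.3 = 1.30 | 0.88 | 8.6% | 8.1% |
| 3 | 0.5 | 1 + 2 × 0.5 = 2.00 | 0.71 | 16.6% | 16.9% |

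**Simulation check.** There were 525 patients, 70% of them admitted, with 1 plus a Poisson number of further stays each. Stay lengths were log-normal (log-scale SD 0.9) with the ICC set on the log scale. There was no arm effect, and each setting had 4,000 runs. At a true rate of 5%, the simulation standard error is √(0.05 × 0.95/4000) = 0.3 percentage points.

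**With the patient as the unit.** In the same simulations, a t-test on total days per patient (zero if never admitted) and a t-test on each admitted patient's mean stay both rejected between about 4% and 5.3% of the time in every setting.

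**ITU.** No test is planned, so only the width ratio applies.

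**The case against.** The strongest reply has four parts.

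*The unit is inferred.* The protocol never says that the observation for the mean stay is the individual stay, and a mean per patient would make the t-test valid in this respect. That is right as far as it goes. But duration is defined per admission, the mean stay is listed apart from the overall duration, and the parallel ITU sentence is explicitly per visit. The per-stay reading is the natural one, though not the only one. A per-patient mean would also be undefined for patients never admitted.

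*The SAP will settle it.* Section 19.2.2 does leave full details to a SAP, which is not among the documents reviewed. Silence on detail would be no finding. Here, however, the protocol names both the measure and the test, and a SAP that follows it faithfully carries the fault forward.

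*Sound measures are already planned.* This stands. Overall duration, frequency, the proportion of patients admitted and patients' overall ITU duration are per-patient summaries and are unaffected. They do not make the per-stay test and intervals beside them valid. The resource-use question in Section 2.1.3 is also better answered by those totals and by the economic analysis in Section 11.2 than by mean length per stay, which limits what is at stake.

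*Few patients will have many stays.* With the protocol's exponential survival and six-month median (Section 19.2.5.1), 0.5^(12/6) = 25% are alive at one year and 0.5^(36/6) = 1.6% at three years. This argues for the lower rows of inflation. It does not remove repeat stays, which the plan foresees.

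A reader might infer that the false-positive rate certainly exceeds 5%, perhaps greatly. The documents do not support that. A separate simulation (262 patients per arm, 2,000 runs) reached 31%, but only with a mean of 3 stays, correlation 0.5 and strongly uneven (Poisson-gamma) numbers of stays together. At correlation 0.05 it gave about 6% to 8%. A reader might also attach a false-positive rate to the ITU item, but no test is planned there.

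**Conclusion.** The point holds on the most natural reading of Section 19.2.2.2. For hospital/hospice stays, the between-arm test is anti-conservative and its interval too narrow if stays are treated as independent, patients have more than one stay, and stays correlate within patient. For ITU visits the per-visit unit is explicit, and the consequence is confined to an interval that is too narrow.

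The size is conditional. Over the assumed range in the table, the rejection rate runs from 5% to about 17%, and the naive interval from full width down to about 0.71 of its correct width. The number of stays and the ICC are assumptions throughout. Because this concerns one companion summary of a secondary outcome, it should be corrected, but it does not threaten the trial's main conclusions or its sample size.

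**What to change.** Add one sentence to Section 19.2.2.2 and carry it into the SAP: the between-arm comparison of hospital/hospice use takes the patient as the unit, using each patient's total days and number of stays, with zero for patients never admitted. Report mean length per stay and per ITU visit descriptively. If an interval or test is wanted for either, use patient-clustered standard errors or a bootstrap that resamples whole patients.

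This needs no new data and no more patients. The small downside is a wider interval for mean length of stay, which is the correct one.
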